#### *Patient Reported Outcomes*

##### Quality of Life

Quality of life will be assessed with the Short Form Health Survey-36 (SF-12), a widely used self-report measure of quality of life and health status. Comprised of 12 multiple choice questions, the SF-12 queries general perceptions a participant has about their health, as well as limitations to physical activity, physical health problems, mental health problems, pain, and energy/fatigue. The SF-12 is used across health research domains, and in breast cancer has been utilized as a longitudinal monitor of quality of life.

Physical activity: The Stanford 7 Day Physical Activity Recall (PAR) interview will be used to estimate participant engagement in physical activity for the 7 days prior to each clinic visit. The PAR assesses the amount of moderate to vigorous PA performed by participants in the preceding week, as well as the amount of time completing both strength and flexibility exercises and hours of sleep each night. The PAR interview has been widely validated and previously used to assess PA outcomes in a home-based exercise intervention for breast cancer survivors.

Sedentary behaviors: Time spent engaging in sedentary behaviors will be measured with the self-administered Sedentary Behaviors Questionnaire (SBQ). The SBQ measures the minutes spent participating in 9 different sedentary behaviors per “typical” weekday and weekend day.

Perceptions of Physical Activity: Participant perceptions of their readiness for physical activity and barriers to successful PA will be captured with an internally developed scale created by combining questions assessing Capability, Opportunity, and Motivation (COM-B) for physical activity and questions assessing perceived barriers to PA that have previously been used in adult cancer survivors.

Perceived well-being: Participants’ perception of their current well-being will be assessed with the 28-item 5-point Likert scale Functional Assessment of Cancer Therapy (FACT)-General. The FACT-G contains 4 subscales measuring physical, social, emotional, and functional well-being and has been validated for reliably measuring well-being in cancer patients.

Insomnia: Participant sleep will be assessed with the Insomnia Severity Index (ISI). The ISI is a 7-item, 5-point Likert scale self-report scale measuring the nature, severity, and effects of insomnia over the previous month. Items are summed to a total score where greater than 7 indicates clinically significant insomnia.

Mood disturbances: Symptoms of anxiety and depression will be assessed with the 4-item, 5-point Likert scale Patient Health Questionnaire (PHQ-4). The PHQ-4 is a brief and validated screener for clinically significant insomnia and depression, and has been used to predict long term physical activity levels in breast cancer survivors.

Fatigue: The Functional Assessment of Chronic Illness Therapy (FACIT)-Fatigue scale is a 13-item scale originally developed for and widely used to assess cancer-related fatigue. The FACIT-Fatigue scale measures severity (e.g., “I feel fatigued”; “I feel weak all over”) and impact of fatigue (e.g., “I need help doing my usual activities”; “I have to limit my social activity because I am tired”) over the past week, with responses scored on a 5-point scale, from 0 “not at all” to 4 “very much.” The FACIT-Fatigue scale has excellent psychometric properties and a focus on physical aspects of fatigue.

#### 4.3 Study Procedures

#### 4.3.1 Recruitment

This project will recruit 30 study participants through a multi-pronged approach:

Seattle Cancer Care Alliance (SCCA) clinics: At SCCA, we will work with the breast oncology clinic research team to obtain a list of potentially eligible research participants that will include patient name, phone number, and mailing address. This eligibility will be based on age and approximate end date of chemotherapy or Herceptin therapy. Potentially eligible participants identified through SCCA will receive a mailed letter endorsed by their oncologist inviting them to call the study coordinator for more information and/or screening. The study team may follow up proactively with a phone call no less than two weeks after sending the letter.

Breast cancer support groups in the community: Study information will be provided to breast cancer support groups in the community by sharing study flyers (paper, electronic, or Web versions) with the organizers of these groups and by giving presentations at in-person group events, as permitted by organizers.

Re-contacting previous breast cancer research participants: The pool of previous breast cancer research participants will be generated from past projects under the purview of the study's principal investigators or shared from affiliate investigators. Previous participants or candidates will be contacted via phone, email, or mailed letter, depending on what information is available to the study PIs.

The UW ITHS Leaf tool: The University of Washington's Leaf system will be used to generate an identifiable cohort of potentially eligible patients in the UW Medicine system. The study will query the database for patients who meet key eligibility criteria and who have recently visited the UW Medicine system for treatment. Candidates generated from this list will be sent a letter that describes the study and invites them to contact the study team should they be interested in participation. The study team may follow up proactively with a phone call no less than two weeks after sending the letter.

#### 4.3.2 Screening

The study coordinator will use the screening script and questionnaire to complete screening (in-person or over-the-phone) of participant eligibility, according to eligibility criteria detailed in section 5.0. Inclusion criterion 4 (reduced CRF) will be estimated with an algorithm based on BMI, resting HR, and self-reported physical activity. Eligible candidates will be given information on the consent process and sent a copy of the consent form for review prior to their baseline visit. Consent will occur at the baseline visit.

#### 4.3.3 Informed Consent Procedures

Candidates will be guided through the written informed consent process. All eligible candidates will be provided the same informed consent. The consent forms will contain the details for all study procedures, including both intervention and waitlist control arms, and for the storage and protection of de-identified data. Participants will be provided with a copy for their records. The consent process will clearly state what type of information will be collected and that all data provided by participants will be confidential. Participants will be assured that all records will be kept confidential in research files

located in a locked office and entered into a password-protected computer located behind a secure and maintained firewall. Candidates will be sent a copy of the consent form prior to their baseline visit for review. They will be encouraged to ask questions prior to or at the beginning of their baseline visit. Consent will be obtained before data collection procedures at the participant's baseline visit.

Consent forms will be reviewed for completeness and stored in a locked file cabinet in a locked office, away from any material with personal or sensitive study data. Participants will be reassured that they can withdraw from the study at any time.

**Comprehension:** Misunderstandings will be addressed in real-time through the teach-back method: During the informed consent process potential participants will be asked to summarize the primary study objective and procedures.

**Ongoing process:** Enrolled participants will have regular communication with study team. The study team will attempt to address any participant concerns over the study that arise in order to strengthen compliance and retention. Ultimately, participants will be reminded that they are volunteering and may withdraw from the study at any time.

#### 4.3.4 Randomization

Participants will be randomly allocated to the intervention or waitlist control arm using blocked randomization (2:1 intervention to control), stratified upon whether the participant has received “AC” chemotherapy (doxorubicin and cyclophosphamide combination therapy). Intervention participants will then be randomized to either aerobic exercise training or resistance strength training, again using blocked randomization stratified on AC treatment history. Randomization will be performed in REDCap with the REDCap Randomization module.

#### 4.3.4 Data Collection

Clinical and self-report data will be collected at 3 total timepoints: baseline, 12 weeks, 24 weeks.

**Self-reported data:** Participants will be asked to complete baseline questionnaires ascertaining demographic information, health history and current health behaviors. At all timepoints (i.e. baseline, 12-, and 24-Week) participants will be asked to complete self-reported questionnaires on quality of life, physical activity, and fatigue.

**Clinic visits:** In-person clinic visits will take place at baseline and 24-weeks for all participants. All clinic visits will include anthropometric assessment, MRI, supervised 6MWT and CPET. Participants will complete a supervised 6MWT. Study procedures will occur at the University of Washington Medical Center and the Fred Hutchinson Prevention Center. At intervention completion participants will be asked open-ended questions regarding their experience with the study. The responses will be analyzed for themes to improve future study designs.

**Passive Data Collection:** Some data will be remotely collected via wrist- and waist-worn actigraphy monitors, worn in the 7 days prior to each clinic visit. Wrist-worn monitors will be worn 24 hours a day including sleep, while waist-worn monitor will be removed for sleep. Wrist-worn devices will also be utilized during all intervention sessions, as a measure of intervention adherence.

Measure	Type of measure	Instrument	Source
Sample Characteristics			
Demographics	Baseline	Questionnaire	Participant
Physical & mental health history	Baseline	Questionnaire	Participant
Intervention Feasibility			
Intervention Feasibility	Primary outcome	Attendance/Retention	Case Report Form
Intervention Acceptability	Secondary outcome	Questionnaire	Participant
Exercise intervention adherence	Other/Exploratory outcome	Actigraphy Monitor	Participant
Exercise intervention adherence	Secondary outcome	RPE	Participant
Intervention session Intensity	Secondary outcome	RPE	Participant
Safety			
Safety	Secondary outcome	Adverse Events	Case Report Form
Cardiorespiratory Fitness			
VO 2 (maximal exercise capacity)	Other/Exploratory outcome	CPET	Case Report Form
Functional Capacity			
6MWD (submaximal capacity)	Other/Exploratory outcome	6MWT	Case Report Form
1 Repetition Maximum (strength)	Exploratory outcome	1-RM	Case Report Form
Physiologic Changes			
Anthropometrics	Other/Exploratory outcome	Physical exam	Case Report Form
Thigh IMF:SM	Other/Exploratory outcome	MRI	Case Report Form
Abdominal fat deposition	Other/Exploratory outcome	MRI	Case Report Form
Patient Reported Outcomes			
Quality of life	Other/Exploratory outcome	SF-12	Participant
Physical activity	Other/Exploratory outcome	PAR/Actigraphy Monitor	Participant
Physical Activity Perceptions	Other/Exploratory Outcome	PA Perceptions & Barriers	Participant
Sedentary behaviors	Other/Exploratory outcome	SBQ	Participant
Perceived well-being	Other/Exploratory outcome	FACT-G Questionnaire	Participant
Insomnia	Other/Exploratory outcome	ISI	Participant
Mood Disturbance	Other/Exploratory outcome	PHQ-4	Participant

Fatigue	Other/Exploratory outcome	FACIT-F	Participant
---------	---------------------------	---------	-------------

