### 4.2 Endpoints

#### 4.2.1 Primary Endpoint

Intervention Feasibility: Intervention feasibility will be determined with all-cause intervention discontinuation rate, which is the proportion of all intervention participants who permanently stop the intervention prior to Week 24 for any reason.

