##### *Study Feasibility & Acceptability*

Study feasibility: Study feasibility will be measured by calculating recruitment rates (proportion of enrolled participants to all individuals approached), lost to follow-up (proportion of participants who do not complete post-intervention assessments), relative dose intensity (proportion of completed to planned sessions), early session terminations (proportion of sessions ended by participant prior to completing planned duration), intervention interruptions (missing 3 or more planned sessions consecutively), attendance (proportion of attended to planned sessions), and adherence (gathered from HR/accelerometry data and self-report of exercise via questionnaires). A benchmark to determine feasibility is <40% loss to follow-up.

Intervention acceptability: Acceptability will be measured with qualitative, open-ended to assess participant experience in the intervention and gather information for improving the protocol in future studies. Of particular attention will be the tolerability of a remote, home-based exercise intervention with a semi-supervised format.

Intervention session intensity and adherence: The Rating of Perceived Exertion (RPE) scale asks respondents to rate the intensity of exercise on a 6 – 20 scale. The measure has been validated for estimating both aerobic and resistance exercise exertion levels, providing a standard measure across intervention modalities. Participants will record RPE after each session in order to track session intensity and completion (adherence).

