In addition, we will explore potential moderators of the intervention, namely baseline BMI and physical activity, and adherence to the intervention for Objectives 2 and 3, and as guidance in designing the subsequent large-scale intervention. First, we will stratify upon BMI to explore whether the intervention showed greater benefit in those with higher BMI. Then we will repeat this for baseline physical activity to explore whether the intervention showed greater benefit in those with lower baseline physical activity. Next, the level of adherence to the intervention will be evaluated by examining the accelerometry data output in conjunction with the self-reported physical activity data. We will also conduct qualitative analyses utilizing data from the elicitation interviews conducted at the end of the intervention. This analysis will summarize data collected from the participants' into themes.

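### The plan does not provide for asking the acceptability questions of participants who permanently stop the exercise program early

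*Combined protocol and SAP*

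**What the plan says.** Section 4.2.2 (Study Feasibility & Acceptability) makes acceptability a secondary, qualitative outcome: "Acceptability will be measured with qualitative, open-ended to assess participant experience in the intervention". Its stated focus is specific: "Of particular attention will be the tolerability of a remote, home-based exercise intervention with a semi-supervised format". It is also meant to inform improvements to the protocol for later studies.

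Two places say when the information is collected. Section 4.3.4 (Data Collection), in the paragraph on clinic visits, reads "At intervention completion participants will be asked open-ended questions regarding their experience with the study". Section 10.0 refers to qualitative work "utilizing data from the elicitation interviews conducted at the end of the intervention". In both, the responses are to be summarized as themes. No score, scale or threshold is given.

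The primary endpoint in Section 4.2.1 is all-cause discontinuation: "the proportion of all intervention participants who permanently stop the intervention prior to Week 24 for any reason".

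The clinic-visit paragraph that sets the timing of the questions also says: "In-person clinic visits will take place at baseline and 24-weeks for all participants".

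**The concern.** The people best placed to say whether the format is tolerable are those who gave it up. The plan counts them in its primary endpoint but describes no point at which they are asked about their experience or their reason for stopping. If the questions reach mainly those who finished, the themes come from a group selected for having tolerated the program.

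Section 10.0 makes the feasibility results a primary consideration in deciding on a larger trial. A discontinuation rate without reasons tells the next team how many stopped, but not whether the schedule, the intensity, the remote delivery or the unsupervised sessions drove them out. That is what a pilot of this kind is well placed to learn.

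**Working it through.** The plan states no acceptability figure and no expected discontinuation rate, so there is nothing to reproduce. The check is a reading of the timing statements, followed by simple arithmetic on how likely the gap is to matter.

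**Inputs from the documents**
- Total sample: 30 (Section 4.3.1).
- Allocation: 2:1 intervention to control (Section 4.1), so 30 × 2/3 = 20 intervention participants.
- Timing of the questions: completion (Section 4.3.4) or end of the intervention (Section 10.0).
- Week 24 visit: planned for all participants (Section 4.3.4).
- Feasibility benchmark: loss to follow-up below 40% (Sections 4.2.2 and 10.0).

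**Step 1: what the timing wording can mean.** It can mean the moment a participant finishes the program (reading A) or the Week 24 timepoint (reading B). Take someone who stops at Week 8, a week chosen only as an example:

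| Participant who stops at Week 8 | Reading A: on finishing the program | Reading B: at the Week 24 visit |
|---|---|---|
| Stays in the study | Not asked | Asked at Week 24, i.e. 24 − 8 = 16 weeks after stopping |
| Leaves the study | Not asked | Not asked |

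On neither reading is anyone asked at the time of stopping. Those who leave are missed on both.

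**Step 2: does another section fill the gap?**
- Section 8.0 has the investigators review premature terminations quarterly, and Appendix A has them review drop-outs monthly. Neither calls for the participant's own reason.
- Adverse-event records would show some stops that followed an injury or symptom, but not stops due to the format or schedule.
- Section 10.0 examines factors related to non-adherence, but the factors it names are baseline measures (well-being, mood, perceptions of activity, fatigue, insomnia). These cannot describe experience during the program.
- Section 4.3.3 promises regular contact with participants about their concerns, but does not make this a data source.

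No section describes an exit interview.

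**Step 3: how likely is it that someone is affected?** The chance of at least one discontinuation among 20 is 1 − (1 − p)^20, where p is an assumed rate:

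| Assumed p | Expected number, 20 × p | Chance of at least one |
|---|---|---|
| 10% | 2 | 1 − 0.9^20 = 88% |
| 20% | 4 | 1 − 0.8^20 = 99% |
| 30% | 6 | 1 − 0.7^20 = more than 99.9% |

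**Step 4: how many could be missed on reading B with the benchmark still met?** If the benchmark is applied to the intervention arm alone (an assumption, since the plan applies it to participants overall), the largest count below 40% of 20 is 7 (7/20 = 35%; 8/20 = 40% fails). That would leave 13 respondents. Loss to follow-up is not the same event as stopping the intervention, so this is only an upper limit on non-response compatible with the benchmark, not a forecast of discontinuation.

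**The case against.** The strongest reply is that the plan does not exclude people who stop. The sentence on timing stands in a paragraph that opens with a Week 24 visit for everyone, and the wording in Section 10.0 can equally describe a point in time. The plan defines stopping the intervention and loss to follow-up separately, and Section 10.0 analyzes the Objective 2 outcomes by assigned arm whatever the adherence, so people who stop are evidently meant to stay and be assessed. This stands. A reader might infer that everyone who discontinues goes unasked, so that acceptability is conditioned on not having the primary-endpoint event. The documents do not support that: someone who stops exercising but attends at Week 24 may well be asked.

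The reply does not remove the gap. Reading B still misses those who leave the study, and it asks the rest only at an in-person visit that may fall many weeks after they stopped. The intent-to-treat statement concerns the Objective 2 outcomes and is not extended to acceptability.

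A second reply is that the table in Section 4.3.4 lists the acceptability instrument as a questionnaire, and Section 4.3.5 schedules questionnaires at Weeks 12 and 24 as well as baseline. This shows that the instrument is described inconsistently (open-ended questions, questionnaire, interviews). It does not place the acceptability items at Week 12: the text of Section 4.3.4 names quality of life, physical activity and fatigue for the repeated questionnaires.

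A third reply is that acceptability would be read beside discontinuation, early session terminations, interruptions and attendance, all of which reflect stopping, and that people who finish can criticize a program too. This also stands. It rules out the inference that the study would report good acceptability however many people stopped.

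**Conclusion.** The concern holds as a gap in the plan. The acceptability questions are timed only at completion or the end of the intervention, and nothing provides for asking participants who permanently stop early. Those who also leave the study would not be asked; those who remain would be asked at best at Week 24. The themes on tolerability will probably be too favorable and will say little about why people stopped.

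The direction rests on the assumption that people who stop view the program less favorably than people who finish. That is likely but not certain; if the two groups hold the same views, nothing is distorted. A reader might want to call this an upward bias of so many percentage points. The documents do not support any such figure, because acceptability is reported as themes without a score and no discontinuation rate is stated. What can be said is that, among 20 intervention participants, at least one discontinuation is very likely at assumed rates of 10% or more, so the gap will probably arise in practice. For a small pilot whose purpose is to shape the next trial, it should be closed.

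**What to change.** In Section 4.3.4 (Data Collection) and Section 10.0, state that all intervention participants are asked the same open-ended questions at intervention completion or at permanent discontinuation, whichever comes first, by phone or video for those who stop. Record the reason for stopping. Present themes separately for completers and discontinuers, and report the numbers asked and answering in each group.

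The cost is a short change of wording and a few brief calls with the existing questions: about 2 to 6 at the assumed discontinuation rates of 10% to 30%. No new instrument is needed. The downside is that some who stop will decline, which is why the numbers asked and answering should be shown beside the themes.

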#### 4.3.5 Schedule of Evaluations

STUDY PROCEDURES	Baseline	Week 12	Week 24
Intervention Arm			
CPET	X		X
MRI	X		X
6MWT	X	X	X
1-RM	X	X	X
Anthropometrics	X	X	X
Questionnaires	X	X	X
Safety (ongoing)	X	X	X
Accelerometry (ongoing)	X	X	X
Control Arm			
CPET	X		X
MRI	X		X
6MWT	X	X	X
1-RM	X	X	X
Anthropometrics	X	X	X
Questionnaires	X	X	X
Safety (ongoing)	X	X	X
Accelerometry (ongoing)	X	X	X

## 5.0 PARTICIPANT SELECTION

*A criterion should be listed as either inclusion or exclusion but not both.*

### 5.1 Inclusion Criteria

1. Age 18 - 75 years, inclusive
2. Female gender
3. Prior diagnosis of invasive breast cancer
4. Completion of chemotherapy or receipt of trastuzumab (Herceptin) therapy within the past 6 – 60 months (0.5 – 5 years)
5. Reduced cardiorespiratory functional capacity, defined as below the median estimated CRF for age/sex-matched controls

